11.3.3. Collection of Pregnancy Information

Pregnancies occurring in participants after enrollment must be reported to Sponsor or designee within 24 hours of the site learning of its occurrence.

Female Participants Who Become Pregnant

- The investigator will collect pregnancy information on any female participant who becomes pregnant while participating in this study. Information will be recorded on the appropriate form and submitted to the Sponsor within 72 hours of learning of a participant's pregnancy.
- The participant will be followed to determine the outcome of the pregnancy (including spontaneous miscarriage, elective termination, normal birth, or congenital abnormality). The investigator will collect follow-up information on the participant and the child, even if the participant is discontinued from the study, and the information will be forwarded to the Sponsor. Generally, follow-up will not be required for longer than 6 to 8 weeks beyond the estimated delivery date. Any termination of pregnancy will be reported, regardless of fetal status (presence or absence of anomalies) or indication for the procedure.
- While pregnancy itself is not considered to be an AE or SAE, any pregnancy complication or elective termination of a pregnancy will be reported as an AE or SAE. Spontaneous miscarriages, congenital anomaly, and/or birth defect abortion should be reported as SAEs.

• Any post-study, pregnancy-related SAE considered reasonably related to the mRNA-1893 by the investigator will be reported to the Sponsor as described in Section 7.1. While the investigator is not obligated to actively seek this information in former study participants, he or she may learn of an SAE through spontaneous reporting.

Any female participant who becomes pregnant while participating in the study will discontinue mRNA-1893 or be withdrawn from the study.

11.4. APPENDIX 4: CDC Working Case Definitions of Myocarditis, Pericarditis, and Myopericarditis Occurring After Receipt of COVID-19 mRNA Vaccines

Table 17: Case Definitions of Probable and Confirmed Myocarditis, Pericarditis, and Myopericarditis

Condition	Definition		
Acute	Probable Case	Confirmed Case	
Myocarditis	Presence of ≥ 1 new or worsening of the following clinical symptoms:* • chest pain, pressure, or discomfort • dyspnea, shortness of breath, or pain with breathing • palpitations • syncope	Presence of ≥ 1 new or worsening of the following clinical symptoms:* • chest pain, pressure, or discomfort • dyspnea, shortness of breath, or pain with breathing • palpitations • syncope	
	 OR, infants and children aged < 12 years might instead have ≥ 2 of the following symptoms: irritability vomiting poor feeding tachypnea lethargy 	 OR, infants and children aged < 12 years might instead have ≥ 2 of the following symptoms: irritability vomiting poor feeding tachypnea lethargy 	
	 AND ≥ 1 new finding of • troponin level above upper limit of normal (any type of troponin) • abnormal electrocardiogram (ECG or EKG) or rhythm monitoring findings consistent with myocarditis§ • abnormal cardiac function or wall motion abnormalities on echocardiogram • cMRI findings consistent with myocarditis¶ 		
	ANDNo other identifiable cause of the symptoms and findings	No other identifiable cause of the symptoms and findings	

Condition	Definition	
Acute Pericarditis**	Presence of ≥ 2 new or worsening of the following clinical features: • acute chest pain ^{††} • pericardial rub on exam • new ST-elevation or PR-depression on EKG • new or worsening pericardial effusion on echocardiogram or MRI	
v 1	This term may be used for patients who meet criteria for both myocarditis and pericarditis.	

Abbreviations: AV = atrioventricular; cMRI = cardiac magnetic resonance imaging; ECG or EKG = electrocardiogram; MRI = magnetic resonance imaging.

Note: An independent Cardiac Event Adjudication Committee (CEAC) comprised of medically qualified personnel, including cardiologists, will review suspected cases of myocarditis, pericarditis, and myopericarditis to determine if they meet Center for Disease Control and Prevention criteria for "probable" or "confirmed" events, (Gargano et al 2021), and provide the assessment to the Sponsor. The CEAC members will be blinded to study treatment. Details regarding the CEAC composition, responsibilities, procedures, and frequency of data review will be defined in the CEAC charter.

[figure not shown]
- * Persons who lack the listed symptoms but who meet other criteria may be classified as subclinical myocarditis (probable or confirmed).
- [†] Using the Dallas criteria (Aretz et al 1987). Autopsy cases may be classified as confirmed clinical myocarditis on the basis of meeting histopathologic criteria if no other identifiable cause.
- § To meet the ECG or rhythm monitoring criterion, a probable case must include at least one of 1) ST-segment or T-wave abnormalities; 2) Paroxysmal or sustained atrial, supraventricular, or ventricular arrhythmias; or 3) AV nodal conduction delays or intraventricular conduction defects.
- ¶Using either the original or the revised Lake Louise criteria. https://www.sciencedirect.com/science/article/pii/S0735109718388430?via%3Dihubexternal icon
- ** https://academic.oup.com/eurhearti/article/36/42/2921/2293375external icon
- ^{††} Typically described as pain made worse by lying down, deep inspiration, or cough, and relieved by sitting up or leaning forward, although other types of chest pain might occur. Reference: (Gargano et al 2021).

11.5. APPENDIX 5: Protocol Amendment History

11.5.1. Amendment 2 (27 Oct 2021)

[figure not shown]

mRNA	Messenger RNA	

otocol mRNA-1893-P201		
Abbreviation	Definition	
nAb	Neutralizing antibody	
NS1	Nonstructural protein 1	
PP	Per-protocol	
PRNT	Plaque reduction neutralization test	
PT	Preferred term	
RT-PCR	Reverse transcription polymerase chain reaction	
SAE	Serious adverse event	
SAP	Statistical analysis plan	
SAS	Statistical Analysis System	
SCR	Seroconversion rate	
SD	Standard deviation	
SOA	Schedule of Assessments	
SOC	System organ class	
TEAE	Treatment-emergent adverse event	
ULOQ	Upper limit of quantification	
WHO	World Health Organization	
WHODD	World Health Organization drug dictionary	
ZIKV	Zika virus	

1. Introduction

This statistical analysis plan (SAP), which describes the planned analyses for Study mRNA-1893-P201, is based on the most recent approved clinical study protocol (CSP), Version Amendment 3, dated 09-Dec-2021. The most recent approved electronic case report form (eCRF) Version 5, dated 07-Oct-2021.

In addition to the information presented in the statistical analysis plan section of the protocol (Section 9) which provides the principal features of analyses for this study, this SAP provides statistical analysis details/data derivations. It also documents modifications or additions to the analysis plan that are not "principal" in nature and result from information that was not available at the time of protocol finalization.

Study mRNA-1893-P201 is a Phase 2, randomized, observer-blind, placebo-controlled, dose confirmation study to evaluate the safety, tolerability, and immunogenicity of Zika vaccine mRNA-1893 in adults aged 18 through 65 years and living in endemic and non-endemic flavivirus areas.

PPD Biostatistics and programming team, designee of Moderna Biostatistics and Programming department, will perform the statistical analysis of the safety, reactogenicity, and immunogenicity data; Statistical Analysis System (SAS) Version 9.4 or higher will be used to generate all statistical outputs (tables, figures, listings, and datasets). The SAP will be finalized and approved prior to the interim analysis database lock when all participants completed their Day 57 visit. If the methods in this SAP differ from the methods described in the protocol, the SAP will prevail.

In this document, subject and participant are used interchangeably; injection of IP, injection, and dose are used interchangeably; vaccination group, treatment group, and treatment arm are used interchangeably.

2. Study Objectives

2.1. Primary Objective

The primary objectives are the following:

• To evaluate the safety, tolerability, and reactogenicity of 2 dose levels of mRNA-1893 Zika vaccine, administered in a 1-dose (μg) or 2-dose schedule (μg or μg dose level) given 28 days apart, in comparison to a placebo control.

• To evaluate the immunogenicity of 2 dose levels of mRNA-1893 Zika vaccine, administered in a 1-dose (CCI μg) or 2-dose schedule (CCI μg or μg of μg dose level) given 28 days apart, as measured by Zika virus (ZIKV)-specific neutralization assay (plaque reduction neutralization [PRNT]), in comparison to a placebo control at Day 57.

2.2. Secondary Objectives

The secondary objectives are the following:

• To evaluate the immunogenicity of 2 dose levels of mRNA-1893, as measured by ZIKV-specific neutralization assay (PRNT and microneutralization [MN]), in comparison to a placebo control, in flavivirus-seronegative participants at baseline and in flavivirus-seropositive participants at baseline.

2.3. Exploratory Objectives

The exploratory objectives are the following:

- To evaluate the duration of the humoral immune response of 2 dose levels of mRNA-1893 at Days 85, 196, 364, 532, and 700, as measured by ZIKV-specific neutralization assay (PRNT and MN), in comparison to a placebo control, in flavivirus-seronegative participants at baseline and in flavivirus-seropositive participants at baseline.
- To evaluate the humoral immunogenicity of 2 dose levels of mRNA-1893, as measured by ligand binding assay, in comparison to a placebo control, in flavivirus-seronegative participants at baseline and in flavivirus-seropositive participants at baseline.
- To evaluate the ZIKV-specific cellular immune response of 2 dose levels of mRNA-1893 in comparison to a placebo control in flavivirus-seronegative participants at baseline and flavivirus-seropositive participants at baseline (cell-mediated immunity [CMI] subset of participants).
- To assess the occurrence of flavivirus infections throughout the entire course of participation in the study in comparison to a placebo control.

3. Study Endpoints

3.1. Primary Endpoints

The primary safety objective will be evaluated by the following safety endpoints:

- Solicited local and systemic adverse reactions (ARs) through 7 days after each investigational product (IP) injection.
- Unsolicited adverse events (AEs) through 28 days after each IP injection.
- Medically attended AEs (MAAEs) throughout the entire study period.
- Serious AEs (SAEs) and adverse events of special interest (AESIs) throughout the entire study period.

The primary immunogenicity objective will be evaluated by either:

- Geometric mean titer (GMT) of ZIKV-specific neutralizing antibodies (nAbs) at Day 57, as measured by PRNT, in all participants, in initially flavivirus-seronegative, and in initially flavivirus-seropositive participants.
- Seroconversion from Day 1 to Day 57.

Seroconversion is defined as either an increase in ZIKV-specific nAb titer from below the lower limit of quantification [LLOQ] to a titer equal to or above LLOQ, or an increase of at least 4-fold in ZIKV-specific nAb titer in participants with pre-existing nAb titers [as measured by PRNT].

3.2. Secondary Endpoints

The secondary objective will be evaluated by the following endpoints:

- GMT of ZIKV-specific nAbs at Days 1, 8, 29, 36, and 57 (Day 57 only for MN), as measured by PRNT and MN.
- GMT of ZIKV-specific nAbs in initially flavivirus-seronegative participants at Days 1, 8, 29, 36, and 57 (Day 57 only for MN), as measured by PRNT and MN.
- GMT of ZIKV-specific nAbs in initially flavivirus-seropositive participants at Days 1, 8, 29, 36, and 57 (Day 57 only for MN), as measured by PRNT and MN.

- Geometric mean fold-rise (GMFR) of ZIKV-specific nAbs in all participants, in initially flavivirus-seronegative and in initially flavivirus-seropositive participants at Days 8, 29, 36, and 57, as measured by PRNT and MN.
- Seroconversion from Day 1 (baseline) to Days 8, 29, 36, and 57 (only for MN), as measured by PRNT and MN.
- Seroresponse at Days 8, 29, 36, and 57 (Day 57 only for MN) in flavivirus-seronegative participants at baseline.
- Increase from baseline of 2-fold or 4-fold in ZIKV-specific nAb titers at Days 8, 29, 36, and 57, as measured by PRNT and MN, in flavivirus-seropositive participants at baseline.

Seroresponse is defined as an increase in ZIKV-specific nAb titer [as measured by PRNT or MN] from below the LLOQ to greater than or equal to the LLOQ.

3.3. Exploratory Endpoints

The exploratory endpoints are the following:

- GMT of ZIKV-specific nAbs at Days 85, 196, 364, 532, and 700, as measured by PRNT and MN.
 - GMT of ZIKV-specific nAbs at Days 85, 196, 364, 532, and 700, as measured by PRNT and MN, in flavivirus-seronegative participants at baseline.
- GMT of ZIKV-specific nAbs at Days 85, 196, 364, 532, and 700, as measured by PRNT and MN, in flavivirus-seropositive participants at baseline.
- GMFR of ZIKV-specific nAbs in all participants, in initially flavivirus-seronegative, and in initially flavivirus-seropositive participants at Days 85, 196, 364, 532, and 700, as measured by PRNT and MN.
- Seroconversion from Day 1 (baseline) to Days 85, 196, 364, 532, and 700, as measured by PRNT and MN.
- Seroresponse at Days 85, 196, 364, 532, and 700, as measured by PRNT and MN, in flavivirus-seronegative participants at baseline.
- Increase from baseline of 2-fold or 4-fold in ZIKV-specific nAb titers at Days 85, 196, 364, 532, and 700, as measured by PRNT and MN, in flavivirus-seropositive participants at baseline.

- Proportion of all participants, of baseline flavivirus-seronegative participants, and
 of baseline flavivirus-seropositive participants with a ZIKV-specific nAb titer equal
 or greater than a nAb titer defined as a protective level in an animal model, at
 baseline, and Days 8, 29, 36, 57, 85, 196, 364, 532, and 700, as measured by
 PRNT.
- Proportion of all participants, of baseline flavivirus-seronegative participants, and of baseline flavivirus-seropositive participants with a ZIKV-specific nAb titer equal or greater than a nAb titer defined as a protective level in an animal model, at baseline, and Days 8, 29, 36, 57, 85, 196, 364, 532, and 700, as measured by MN.
- Geometric mean concentration (GMC) of ZIKV-specific serum ligand binding antibodies (bAbs) at Days 1, 8, 29, 36, 57, 85, 196, 364, 532, and 700, as measured by ligand binding assay.
- GMC of ZIKV-specific bAbs at Days 1, 8, 29, 36, 57, 85, 196, 364, 532, and 700, as measured by ligand binding assay, in flavivirus-seronegative participants at baseline.
- GMC of ZIKV-specific bAbs at Days 1, 8, 29, 36, 57, 85, 196, 364, 532 and 700, as measured by ligand binding assay, in flavivirus-seropositive participants at baseline.
- Seroconversion from Day 1 (baseline) to Days 8, 29, 36, 57, 85, 196, 364, 532, and 700, as measured by ligand binding assay.
- Seroresponse at Days 8, 29, 36, 57, 85, 196, 364, 532, and 700, as measured by ligand binding assay, in flavivirus-seronegative participants at baseline.
- Increase from baseline 2-fold or 4-fold in bAb concentrations at Days 8, 29, 36, 57, 85, 196, 364, 532, and 700, as measured by ligand binding assay, in flavivirus-seropositive participants at baseline.
- Frequency of ZIKV-specific T cells at Days 1 (baseline), 29, 36, 57, 196, 364, 532, and 700, as measured by intracellular cytokine staining assay and sequencing (CMI subset of baseline flavivirus-seronegative and -seropositive participants).
- Frequency of ZIKV-specific B cells at Days 1 (baseline), 29, 36, 57, 196, 364, 532, and 700, as measured by ELISpot (CMI subset of baseline flavivirus-seronegative and -seropositive participants).

- Additional assays to profile the T- and B-cell responses may also be performed (CMI subset of baseline flavivirus-seronegative and -seropositive participants).
- Seroconversion (ZIKV NS1-specific bAbs) from Day 1 (baseline) to Days 29, 57, 85, 196, 364, 532, and 700

Seroconversion for ZIKV NS1-specific bAbs is defined as the change to a positive ZIKV NS1-specific bAbs status from a baseline negative ZIKV NS1-specific bAbs status.

[figure not shown]
4. Study Design

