- Seroresponse is defined as an increase in ZIKV-specific bAb concentration from below the LLOQ to greater than or equal to the LLOQ (as measured by ligand binding assay).
- Seroconversion is defined as an increase in NS1-specific bAb concentration from below the LLOQ to a concentration equal to or above the LLOQ, or an increase of at least 4-fold in NS1-specific bAb concentration as measured by ELISA.

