8.3.2. Efficacy Assessments

Blood samples for detection of asymptomatic flavivirus infection will be collected as described in Table 1 and Table 2. Asymptomatic flavivirus infections will be assessed through quantification of nonstructural protein 1-specific bAbs, as measured by enzyme-linked immunosorbent assay (ELISA).

In case of signs or symptoms suggesting a flavivirus infection (mostly dengue and Zika in the areas where the study will be performed), an additional blood sample will be collected to confirm the diagnosis via specific serology (IgM antibody capture ELISA and virus neutralization assay) and RT-PCR.

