6.1. General Considerations

The Schedule of Assessments is provided in Appendix E for the vaccination period and the follow-up period, and Appendix F for the extension period.

Continuous variables will be summarized using the following descriptive summary statistics: the number of subjects (n), mean, standard deviation (SD), median, minimum (min), and maximum (max).

Categorical variables will be summarized using counts and percentages.

Baseline value, unless specified otherwise, is defined as the most recent non-missing measurement (scheduled or unscheduled) collected before the first dose of IP. For immunogenicity tests, the baseline is defined as the most recent non-missing measurement (scheduled or unscheduled) collected before or on the date of first dose of IP.

For the summary statistics of all numerical variables unless otherwise specified, the display precision will follow programming standards. Please see Appendix A for variable display standards.

When count data are presented, the percentage will be suppressed when the count is zero in order to draw attention to the non-zero counts. A row denoted "Missing" will be included in count tabulations where specified on the shells to account for dropouts and missing values. The denominator for all percentages will be the number of subjects in that vaccination group within the analysis set of interest, unless otherwise specified.

Study day relative to the first injection will be calculated as below:

a) study day prior to the first injection will be calculated as: date of assessment/event
 date of the first injection;

b) study day on or after the date of the first injection will be calculated as: date of assessment/event – date of the first injection + 1;

Study day relative to the most recent injection will be calculated as below:

- a) study day prior to the first injection will be calculated as: date of assessment/event
 date of the first injection;
- b) study day on or after the date of the first injection but before the second injection (if applicable) will be calculated as: date of assessment/event date of the first injection + 1;
- c) study day on or after the date of the second injection will be calculated as: date of assessment/event – date of the second injection + 1; if study day is on the same day as the second injection, date and time will be compared with the second injection date and time.

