- Proportion of seroconversion in ZIKV-NS1 specific bAbs at Days 29, 57, 85, 196, 364, 532, and 700, as measured by ELISA will be tabulated with 2-sided 95% Clopper-Pearson CIs. The difference of the seroconversion rates between each mRNA-1893 group and placebo group will be provided with 2-sided 95% CIs using the Miettinen-Nurminen method.

Reverse cumulative curves will be provided for ZIKV-specific nAb titers, as measured by PRNT and MN. Similar analyses will be performed for ZIKV-specific bAbs as measured by ligand binding assay.

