6.6. Planned Analyses

The following analyses will be conducted on cleaned data:

- 1. An IA of safety and immunogenicity data will be performed after all participants have completed Day 57 (28 days after the IP injection). Analysis of nAbs will include baseline, Day 29 and Day 57 visits; Analysis of other immunogenicity data will depend on data availability at the time of analysis. The IA will be performed by a separate team of unblinded programmers and statisticians. Pre-identified Sponsor team members will be unblinded to review treatment level results, as defined in the study Data Blinding Plan. The unblinded statistics team will not be involved in either study design or the regular study conduct. The participants and study sites will remain blinded until the conclusion of the study. The IA will serve as the basis for the progression to the ZIKV Phase 3 studies.
- 2. The final CSR will include full unblinded analyses of all safety and immunogenicity with individual unblinded listings through Day 196 (all data through approximately 6 months after the last IP injection). Note that safety data will be reported cumulatively up to the cutoff date, and immunogenicity data will be reported for each participant up to their Day 196 visits.

3. An addendum to the CSR will include the safety and immunogenicity data from Month 8 until EOS for all participants enrolled in the Extension Period.

In addition, unblinded data presentation or analysis for DSMB review will be handled by the unblinded team of statisticians and programmers, who are not involved in study design. More details regarding DSMB analysis can be found in the DSMB Charter.

7. Changes from Planned Analyses in Protocol

Not applicable.

8. References

Department of Health and Human Services (DHHS), Food and Drug Administration, Center for Biologics Evaluation and Research (US). Guidance for industry: Toxicity grading scale for healthy adult and adolescent volunteers enrolled in preventative vaccine clinical trials. September 2007 [cited 2019 Apr 10] [10 screens].

Available from:

https://www.fda.gov/downloads/BiologicsBloodVaccines/GuidanceComplianceRegulatory Information/Guidances/Vaccines/ucm091977.pdf.List of Appendices

9. List of Appendices

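### The SAP drops the protocol's 4-fold limb from NS1 seroconversion but leaves baseline NS1-positive participants in the denominator, which dilutes the reported rate and risk difference

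*SAP*

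**What the plan says.** **Purpose of NS1.** Protocol Section 8.3.2 states: "Asymptomatic flavivirus infections will be assessed through quantification of nonstructural protein 1-specific bAbs". This serves the exploratory objective on the occurrence of flavivirus infection in comparison with placebo.

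**Protocol definition.** The notes to Table 5 (Protocol Section 3.3) accept a rise from below the LLOQ to the LLOQ or above, "or an increase of at least 4-fold in NS1-specific bAb concentration as measured by ELISA". Table 5 also lists the geometric mean concentration of NS1 antibody as an endpoint.

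**SAP definition.** SAP Section 3.3 keeps only the "change to a positive ZIKV NS1-specific bAbs status from a baseline negative ZIKV NS1-specific bAbs status". It has no fold-rise limb, and the NS1 geometric mean concentration is no longer among the endpoints.

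**SAP analysis.** Section 6.4.4 tabulates the "Proportion of seroconversion in ZIKV-NS1 specific bAbs at Days 29, 57, 85, 196, 364, 532, and 700, as measured by ELISA" with Clopper-Pearson intervals, and adds a Miettinen-Nurminen difference between each vaccine group and placebo. It states no restriction by baseline NS1 status.

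**Denominator.** Section 6.1 sets the default: "The denominator for all percentages will be the number of subjects in that vaccination group within the analysis set of interest, unless otherwise specified".

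**Precedence.** SAP Section 1 says the SAP prevails where it differs from the protocol. Section 7, "Changes from Planned Analyses in Protocol", is marked as not applicable.

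**The concern.** Under the SAP definition, a participant who is NS1-positive at baseline cannot become an NS1 seroconverter. If that participant stays in the denominator, he or she is a built-in non-event. The percentage is then neither a rate among people who could show the event nor the rate the protocol described.

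Elsewhere the SAP guards against this. Neutralizing-antibody seroconversion keeps a 4-fold limb for participants with pre-existing titers. Seroresponse, which counts only a crossing of the LLOQ, is confined to participants who are flavivirus-seronegative at baseline. NS1 seroconversion has neither safeguard.

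At stake is the reading of the planned measure of asymptomatic infection, and of its difference from placebo. A reader of the report would not learn from Section 7 that the definition had changed.

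**Working it through.** The documents state no NS1 prevalence, infection rate or power for this endpoint, so there is no planned figure to reproduce. The effect can be shown algebraically.

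**Quantities (none given in the documents)**
- q: share of participants NS1-positive at baseline, taken as equal across arms.
- a: NS1 seroconversion rate among baseline NS1-negatives (the at-risk rate), assumed 5%.
- b: rate among baseline-positives of infections that show as a rise of at least 4-fold, taken as 0, 2.5% or 5%.

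Two simplifications apply. Everyone has a result at the visit, and NS1-positive is treated as the same as at or above the LLOQ. The SAP does not say how these two thresholds relate.

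**Formulas**
- SAP rule, default denominator: a(1 − q)
- SAP rule, baseline NS1-negatives only: a
- Protocol rule, all participants: a(1 − q) + bq

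For example, at q = 50% the SAP rule gives 5% × 0.50 = 2.5%. The protocol rule with b = 2.5% gives 2.5% + 2.5% × 0.50 = 3.75%.

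| q | SAP rule, all | SAP rule, NS1-negatives only | Protocol rule, b = 0 | Protocol rule, b = 2.5% | Protocol rule, b = 5% |
|---|---|---|---|---|---|
| 10% | 4.5% | 5% | 4.5% | 4.75% | 5% |
| 25% | 3.75% | 5% | 3.75% | 4.375% | 5% |
| 50% | 2.5% | 5% | 2.5% | 3.75% | 5% |
| 75% | 1.25% | 5% | 1.25% | 3.125% | 5% |

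**Against the at-risk rate**, the SAP figure is too low by the factor (1 − q): 0.90, 0.75, 0.50 and 0.25.

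**Against the protocol rule**, the loss depends on b as well. There is none at b = 0, and it is the full factor (1 − q) at b = a.

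**Comparison with placebo.** Take assumed at-risk rates of 5% on placebo and 2.5% on vaccine, a difference of 2.5 points. The reported difference is 2.5 × (1 − q), that is 2.25, 1.875, 1.25 or 0.625 points. The ratio is 2.5(1 − q) / 5(1 − q) = 0.50 at every q.

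**Whether other planned outputs recover the loss**
- SAP Section 6.5 counts post-baseline dengue or Zika PCR positives in the FAS, whatever the baseline NS1 status. Under Protocol Section 8.3.2 the sample for that test is taken when signs or symptoms suggest infection, so asymptomatic infection is not recovered.
- The NS1 positive and negative proportions by visit (SAP Section 6.4.4) cannot show a rise in someone already positive.
- Displays by flavivirus serostatus do not isolate those at risk, because serostatus rests on dengue and West Nile IgG and IgM (SAP Section 6.1), not on ZIKV NS1.

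**The case against.** **The denominator is inferred.** Section 6.1 allows exceptions, and the NS1 definition itself starts from a negative baseline, so a programmer might restrict the denominator. This is fair as a description of the text. But no NS1-specific exception is written, so the default governs.

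**Baseline-positives can still count as infected.** A reader might infer that they never can. The documents do not support that, because PCR-confirmed dengue or Zika counts under SAP Section 6.5. The loss is confined to asymptomatic or PCR-missed infection in baseline-positives.

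**Understatement of infection is not automatic.** A reader might take (1 − q) as the shortfall in true infection. That requires baseline-positives to be infected, with a rise of at least 4-fold, as often as negatives seroconvert. With b = 0 the SAP and protocol rules agree.

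**A particular problem in Puerto Rico is supposition.** The protocol assumes that most flavivirus-seropositives will come from there, but it gives no ZIKV NS1 prevalence for any region.

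**The consequences are limited.** The endpoint is exploratory, the study tests no hypotheses, and randomization should balance q, so little bias is expected in the ratio. This stands and keeps the point modest.

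**The 4-fold limb may not be recoverable.** The SAP tabulates NS1 only as positive or negative and drops the concentration endpoint, which suggests a qualitative reading. In that case the remedy is the restricted denominator.

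**Conclusion.** The point holds in limited form. The SAP narrows the NS1 seroconversion definition without declaring it. Followed as written, it also includes participants who cannot have the event. As at-risk quantities, the reported percentage and risk difference are multiplied by (1 − q), for instance halved at q = 50%. The size is unknown because q is not in the documents.

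Measured against the protocol's own rule, the shortfall lies anywhere between nothing and the full factor (1 − q), depending on how often baseline-positives have infections that show as a rise of at least 4-fold. The ratio between arms should be little affected if q is balanced.

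The documents do not support the broader conclusion that infection in the trial is understated by a known amount. The primary and secondary immunogenicity endpoints are not involved. The correction is worth making because it is cheap and no other planned output supplies the missing information.

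**What to change.** - If the NS1 assay gives quantitative results, restore the limb for a rise of at least 4-fold in participants positive at baseline.
- Otherwise, state in SAP Section 6.4.4 that the NS1 seroconversion proportion and the Miettinen-Nurminen difference are computed among baseline NS1-negative participants with a result at that visit. Report baseline-positives separately as not evaluable for NS1 seroconversion.
- List in SAP Section 7 whatever departure from the protocol remains, including the omitted NS1 geometric mean concentration.

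The cost is a few lines of text and one denominator flag. Restricting the denominator also widens the interval, possibly a great deal in flavivirus-seropositives. With about 100 per arm and an assumed q of 80%, 100 × 0.20 = 20 would remain. At an observed 5%, the Clopper-Pearson interval goes from 1.6% to 11.3% (5 of 100) to 0.1% to 24.9% (1 of 20). That width reflects how many participants can show the event.
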